Protocol Number: NP-PWD-02

Protocol Date and Version #:09 February 2024, V2

PROTOCOL TITLE: A Case-Control Study of Negative Pressure Platform Wound Devices (NP-PWD) for Skin and Soft Tissue Defects

SECTION A: RESEARCH TEAM AND LOCATIONS

A1. RESEARCH TEAM

Study Role	Institution/Company and Contact Information
Principal Investigator and Sponsor	[name] Principal Investigator The Metis Foundation [contact] [contact]
Key Research Personnel	[name] Research Project Manager The Metis Foundation [contact] [contact]
	[name] Clinical Research Nurse The Metis Foundation [contact] [contact]

A2. RESEARCH LOCATIONS

Northeast Baptist Hospital

A3. MULTISITE RESEARCH N/A

B. SOURCE OF EXTERNAL FUNDING

Applied Tissue Technologies

C1. HYPOTHESIS/STUDY SYNOPSIS

Hypothesis: The Negative Pressure Platform Wound Device (NP-PWD) technology is a feasible alternative to manage skin and soft tissue defects as compared to standard of care, KCI Wound VAC granulofoam.

Study Synopsis: This study will demonstrate the effectiveness of the NP-PWD therapy in managing complex wounds and improving wound healing parameters as compared to standard of care.

A study of 24 completed subjects will be conducted by enrolling patients who are requiring treatment for open skin and soft tissue defects. Patients will be screened for inclusion criteria and asked to consent to participate in the study. Following consent subjects will be randomized to receive treatment of one of the two study arms. Arm 1, the standard of care arm, will receive KCI Wound VAC Granulofoam. Arm 2, the study arm, will receive treatment with NP-PWD. Prior to the initial application, wound evaluations and photography will be completed to include assessment of infection with wound swabs. The wound dressing will be assessed for the need for change every 2-3 days and changed if clinically indicated (following each device IFU). Subjects will be followed for up to nine days post initial application. At minimum, the randomized treatment will be applied for 2 days after initial application for a subject to be considered completed. Subject who do not complete the treatment course (minimum of 2 days of treatment), may be replaced per investigators discretion. Follow up data will be gathered at each change/removal of the NP-PWD or Wound VAC. The data collected will include indications for dressing change, dressing change process, photographs and assessments for wound healing, infection, and adverse events. Gathered clinical data of the enrolled subjects will be used to evaluate the feasibility in using the NP-PWD device for wound healing management.

C2. BACKGROUND

Open complex wounds are a prominent issue, as unhealed or untreated wounds pose a risk of microbial infection. The Negative Pressure Platform Wound Device or NP-PWD, is an innovative therapy which uses a patented dressing to promote healing by creating a vacuum (negative pressure) at the wound site without the use of an intervening foam dressing. This pressure promotes granulation of the skin, forming new connective tissue and blood vessels, removes or inhibits microbial and infectious agents, as well as pulls wound edges together for closure. Although this therapy is evolving, the review of elements and effects on wounds is still uncertain and requires further studies regarding the mechanism and use of NP-PWD in wound healing.

C3. OBJECTIVES/STUDY GOALS

This study is intended to evaluate the feasibility of the NP-PWD as compared to SOC for the treatment of wound healing through assessment of healing time, feasibility of application, patient

comfort, and adverse events.

Primary:

To determine the usability and feasibility of NP-PWD in comparison to SoC

Secondary:

- To evaluate and compare wound readiness for closure between study wounds treated with NP-PWD versus SoC
- To evaluate colony forming units present on study wounds before and after treatment(s)
- To evaluate the ease of use of the product by healthcare providers
- To evaluate tolerability of the product by patient subjects

C4. SUBJECT SELECTION

Twenty-four (24) patients, 18 years of age or older, who are requiring treatment for open skin and soft tissue defect at a hospital within the Baptist Health System will be recruited for participation in this study. Potential subjects must meet the following inclusion and exclusion criteria to be included in this study.

Inclusion Criteria

All subjects enrolled must meet ALL the following criteria:

1. Patients 18 years of age or older of either gender
2. Have an open skin or soft tissue defect requiring treatment

Exclusion Criteria

Subjects who meet any of the following criteria will be excluded from the study:

1. Active malignant disease at the study site
2. Any concomitant medications or co-morbidities that, in the opinion of the investigator, may interfere with device use
3. On any investigational drug(s) or therapeutic device(s) to the study site in the last 30 days or any previous enrollment in this study
4. Pregnant at enrollment

When a potential subject is identified a member of the research staff will approach the potential subject or their legally authorized representative (LAR) and introduce the proposed study. If a potential subject or their LAR expresses interest in participation in the study, the PI or designated study personnel will proceed with the informed consent process for potential enrollment.

D. STUDY PROCEDURES/ RESEARCH METHODS

Informed consent of potential subjects will be done in a quiet and private area of the patient care setting (hospital or clinic office) to ensure patient confidentiality. The PI or designated study staff will discuss and explain elements of the study with the informed consent document. The PI or designated study staff will also be available to answer questions for the potential subject.

A copy of the IRB-approved informed consent document will be given to the potential subject for their review and ample time will be given for their decision making. If the potential subject decides to participate, the IRB-approved informed consent document will be signed and dated appropriately by all persons required on the document. The original signed consent document will be kept in the study files; a copy will be given to the subject and a copy will be placed in the subject's medical record.

Study procedures will not begin until eligibility is determined, and the informed consent process is completed. Patients who sign the informed consent form are considered to be enrolled. If a patient signs the consent but is not randomized into the study, the patient is considered a screen failure.

Subjects will be enrolled for up to 9 days following application of the NP-PWD or Wound VAC. At minimum, the randomized treatment will be applied for a minimum of 2 days after initial application for a subject to be considered completed. Subject who do not complete the treatment course (minimum of 2 days of treatment), may be replaced per investigators discretion.

Activities to be completed for each visit are as follows:

Treatment (Day 0): Screening, consent, documentation of baseline demographics, medical history and physical, measurement and photography of wound, wound swab for colony forming unit count, randomization, and application of NP-PWD or Wound Vac according to randomization.

Follow-up visits:

At each follow-up visit the study wound will be assessed for the need for dressing change (every 2-3 days) and changed if clinically indicated (following the respective device's IFU). The study wound sites will be assessed for signs of infection, erythema, itching, drainage, quality of closure and pain.

Follow-up (Visit 2): Assessment of need for dressing change and completion of change of treatment dressing if necessary. Should the study subject's wound indicate continuation of negative pressure wound therapy a second application of the randomized treatment may be applied. If the subject no longer requires negative pressure wound therapy, the therapy will be

discontinued. Wound assessments, measurements, photographs, assessments for adverse events will all be completed and documented.

Optional Follow-up (Visit 3 & 4): Assessment of need for change of treatment dressing, reapplication if necessary or removal, wound assessment, measurements, photographs, assess for adverse events.

If negative pressure wound therapy is no longer indicated at any time after the minimum requirement of 2 has been met, the therapy will be discontinued and assessments will be completed to include a final wound swab, and the subject's participation will end.

[figure not shown]
Schedule of Events

Research Procedures	Visit 1 Day 0	Visit 2 Day 2-3	Visit 3 Day 5-6 (Optional)	Visit 4 Days 7-9 (Optional)
Assessment of Eligibility	X			
Informed Consent	X			
Demographics and H&P	X			
Wound assessment	X	X	X	X
Photography	X	X	X	X
Randomization	X			
Assessment of need for dressing change		X	X	X
Treatment application	X	X*	X*	
Wound swab (CFU) [^]	X			X
Adverse event assessment	X	X	X	X

*At minimum the treatment will be applied once but can be applied up to three times. Visits 3 and 4 are optional.

^ The wound swab will be taken once at baseline and once at the time of final removal.

Study Intervention Flow Chart

Data Collection

Data collection will consist of data collection worksheets. All information collected about subjects during the study will be kept strictly confidential and will be maintained in a secure, locked file and accessed only by study staff. Data will be entered into a secured, password-protected database. Upon completion of the study, records will be archived in a password-protected file on a Metis server. Subject names will not appear in any reports or published articles.

Subjects will be assigned and identified by a sequential study number to protect the confidentiality of the subject. All information collected about subjects during the study will be kept strictly confidential. Subject names will not appear in any reports or published articles. Materials that identify subjects as individuals including medical records will not be released without the subject's explicit permission as required by law.

Subjects will be made aware that their medical records, which identify them as individuals, may be inspected by the designated IRB and/or other applicable regulatory authorities.

Data Analysis

All pertinent data will be analyzed using descriptive and correlational statistics as appropriate to compare those patients who were treated. Overall standard descriptive statistical methods will be used to analyze other data; any categorical variables will be compared via chi square analysis while continuous variables will be compared via student-t test or Wilcoxon test as appropriate. We plan to perform a forward stepwise logistic regression. The available data including patient specific data as well as treatment variables will first be evaluated using a univariate analysis for possible significant risk factors. These will then be analyzed using a multiple logistic regression analysis and tested for interaction.

D1. RISK/ SAFETY INFORMATION

Risks of harm, measures to reduce the risks of harm and benefits of participation

Risks of Harm

Research Procedure Name: Application of NP-PWD or Wound VAC

Research Procedure Description: Application of a NP-PWD or Wound VAC onto open wound.

Research-related Risks

- Itching, swelling and redness.
- Infection.

- Poor healing.

Measures to Minimize Risks of Harm: (Precautions, safeguards): Application of the NP-PWD or Wound VAC will be performed in a controlled clinical setting. Throughout the course of the study, the NP-PWD or Wound VAC will only be applied by trained professionals and the site will be monitored for signs adverse reactions such as infection or poor healing.

D2. MONITORING AND REPORTING OF ADVERSE EVENTS/ SERIOUS ADVERSE EVENTS

Monitoring

Data collected on the subjects will be entered into a data spreadsheet that will be verified routinely by designated study personnel for accuracy and completeness. The study will be conducted in compliance with any applicable laws and regulations. Designated study staff, for accuracy and completeness, will verify data collected. All regulatory and subject files will be maintained in accordance with any applicable regulations.

The principal investigator will be responsible for the protocol safety monitoring. The PI will make study documents (e.g., consent forms, data pulls) and pertinent hospital or clinical records readily available for inspection by the IRB and oversight staff for confirmation of the study data.

Adverse Events

Adverse events that are anticipated in this patient population include those associated with wound healing.

Unexpected adverse events and unanticipated problems

All unanticipated problems involving risks to subject or others will be promptly reported to the IRB by email. A complete written report will follow the initial notification.

Adverse Device Effects

Unanticipated adverse device effects (UADE) are any serious adverse effect on health or safety or any life-threatening problem or death caused by, or associated with, a device, if that effect, problem, or death, was not previously identified in a nature, severity, or degree of incidence in the investigational plan or application (including a supplementary plan or application), or any other unanticipated serious problem associated with a device that relates to the rights, safety, or welfare of subjects.

UADEs must be reported by the clinical investigator to the sponsor and the reviewing IRB. For device studies, investigators are required to submit a report of a UADE to the sponsor and the reviewing IRB as soon as possible, but in no event later than 10 working days after the investigator first learns of the event (21 CFR 812.150(a)(1). Sponsors must immediately conduct an evaluation of a UADE and must report the results of the evaluation to FDA, all reviewing IRBs, and participating investigators within 10 working days after the sponsor first receives notice of the effect (21 CFR 812.46(b), 812.150(b)(1).

D3. CONFIDENTIALITY

PRIVACY FOR SUBJECTS

Discussion of the study with the potential subject and the Informed consent process will be done in a quiet and private area of the hospital to ensure privacy.

Subjects will be made aware that their research records, which identify them as individuals, may be inspected by applicable regulatory authorities, to ensure the integrity of the data and/or to protect research participants.

CONFIDENTIALITY PROCEDURES FOR RESEARCH RECORDS, DATA

To protect subject confidentiality, subjects will be identified using an assigned study ID number that will be used on study documents. The key linking subjects' identities will be electronically stored by the research team on a password protected secured database, separate from other study data. All information collected about subjects during the study will be kept strictly confidential and will be maintained in a secure, locked file accessible only by study staff. Signed informed consent forms will be kept no fewer than three years, and no fewer than 6 years for signed HIPAA authorizations. Upon completion of the study, records will be archived in a password-protected file on an ISR network server. Thereafter, the key linking subject identifiers to study ID numbers will be destroyed, rendering the data permanently de-identified. Subject names will not appear in any reports or published articles.

Electronic data to include, but not limited to, information gathered from the electronic medical records and stored data entries will be stored on a password protected file. Locked subject study records will only be accessed by research personnel assigned to the protocol.

D4. INTENDED USE OF DATA

The data collected for this study will be used to determine the feasibility of the NP-PWD use as compared to SOC in the treatment of complex wounds. The intentions are to present the findings at a professional conference/meeting and/or via publication. All data presented or published will be de-identified keeping the identity of the subjects will be protected.

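### The hypothesis is that NP-PWD is a feasible alternative to standard of care, but the arms are compared only by tests of difference, with no between-arm estimate or interval; a non-significant result cannot support the hypothesis and could be misread as doing so

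*Combined protocol and SAP*

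**What the plan says.** The one statement labelled a hypothesis, in C1, is that NP-PWD "is a feasible alternative to manage skin and soft tissue defects as compared to standard of care". The Study Synopsis directly below it adds a different kind of aim, "improving wound healing parameters as compared to standard of care". The primary objective in C3 is "To determine the usability and feasibility of NP-PWD in comparison to SoC", and D4 says that the data "will be used to determine the feasibility of the NP-PWD use as compared to SOC".

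On size and design, C1 says "A study of 24 completed subjects will be conducted" and that "subjects will be randomized to receive treatment of one of the two study arms". The allocation ratio, significance level and power are not given.

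Data Analysis (section D) provides for descriptive and correlational statistics, then states that "any categorical variables will be compared via chi square analysis while continuous variables will be compared via student-t test or Wilcoxon test", and adds a forward stepwise logistic regression. It specifies no between-arm difference, confidence interval, margin or feasibility threshold, and no rule for reading a significant or a non-significant result.

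**The concern.** Calling a device a feasible alternative as compared to standard of care is a comparative claim. C3 lists healing time, feasibility of application, patient comfort and adverse events as the means of assessing it, and on these a worse device would matter. Chi-square, t and Wilcoxon tests all take no difference as the null hypothesis. Rejecting it can show that the arms differ. Failing to reject it does not show that they are alike, least of all with 24 subjects.

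The output that would speak to the hypothesis is an estimate of the difference with its uncertainty, because it shows how much worse NP-PWD could still be. The plan does not ask for one. A set of non-significant p-values could then be presented as support for the hypothesis at a conference or in a paper, which D4 names as the intended use, although the data might be compatible with a large deficit.

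**Working it through.** **Inputs from the protocol.** 24 completed subjects and two randomised arms (C1); chi-square, t or Wilcoxon tests (Data Analysis). Non-completers may be replaced, so 24 is taken as the analysed number. The 24 cannot be reproduced, because no effect size, SD, rate, significance level or power is given for it.

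**Assumptions.** 1:1 allocation (12 per arm) and two-sided 0.05. The deficits and success rates below are illustrative and are shown as a range.

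**1. Continuous outcome, t-test.** Degrees of freedom are 12 + 12 − 2 = 22, and the critical value is 2.074. For a true deficit of d SD the noncentrality is d / √(1/12 + 1/12) = d / 0.408. The chance of p ≥ 0.05 is one minus the power from the noncentral t distribution.

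| True deficit | Power | Chance of p ≥ 0.05 |
|---|---|---|
| 0.5 SD | 0.216 | 78% |
| 0.8 SD | 0.466 | 53% |
| 1.0 SD | 0.649 | 35% |
| 1.2 SD | 0.802 | 20% |

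Power passes 50% only at about 0.84 SD.

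**2. Binary outcome.** All 13 × 13 possible results for 12 against 12 were enumerated and their binomial probabilities summed wherever p ≥ 0.05. The plan does not say whether chi-square is continuity-corrected. In these cases the corrected version gives the same figures as Fisher.

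| True success, SoC v NP-PWD | Uncorrected chi-square | Fisher or corrected |
|---|---|---|
| 80% v 60% | 82% | 91% |
| 80% v 50% | 64% | 79% |
| 90% v 60% | 61% | 77% |
| 80% v 40% | 43% | 61% |
| 90% v 40% | 21% | 36% |

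**3. What an interval would show.** Suppose 8/12 succeed on NP-PWD and 11/12 on standard of care. Uncorrected chi-square = 24 × (8×1 − 4×11)² / (12 × 12 × 19 × 5) = 2.27, p = 0.13. The difference is 0.667 − 0.917 = −25 points, with Newcombe 95% CI −53 to +8 points. The p-value alone says not significant. The interval says that NP-PWD could be up to 53 points worse.

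**4. Precision at this size.** The 95% CI half-width for a continuous outcome is 2.074 × √(2/12) = 0.85 SD. For proportions it is roughly 1.96 × √(2p(1−p)/12): 24 points at p = 90%, 32 at 80% and 37 at 70%.

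**5. Sensitivity to allocation.** With an 8:16 split, power falls to 0.197 at 0.5 SD and 0.424 at 0.8 SD, so p ≥ 0.05 occurs 80% and 58% of the time. Equal allocation is the favourable assumption.

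**The case against.** Several stronger readings are tempting, and the documents do not support them.

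- *That the plan will count p > 0.05 as success.* A reader might infer this, but no section gives any interpretation rule. The gap leaves the misreading open; it does not prescribe it.
- *That the hypothesis is one of non-inferiority or equivalence.* The protocol uses neither term. Feasibility and usability could in part be judged descriptively. However, the hypothesis, the primary objective and D4 are all worded against standard of care, and no descriptive criterion is given either.
- *That tests of difference are wrong for the whole trial.* The Synopsis also aims to show improved healing, and such tests have the right form for that aim, though with little power here. They still do not address the labelled hypothesis.
- *That nothing but tests is planned.* Descriptive statistics would let a reader see the observed difference, though not its precision. The logistic regression could yield effect estimates, but its outcome is not named and its terms are chosen by stepwise selection, so an estimated treatment effect is not assured.
- *That non-significance is likely however bad the device is.* It is not. At a deficit of 1.0 SD, or for 40% against 90% success, a significant result is the more likely one. At 40% against 80% it depends on which test is used.

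It is also fair to say that intervals do not supply what C1 and C3 leave undefined, namely a primary endpoint and a feasibility criterion. That gap remains and is separate from this point.

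**Conclusion.** The point holds in a limited form. The only direct between-arm comparison that Data Analysis specifies is by tests of difference. Their non-significant results cannot support the hypothesis in C1, and the plan has no safeguard against reading them that way. With 12 per arm and two-sided 0.05, both assumed, a non-significant result is more likely than not for true deficits up to about 0.8 SD, or about 30 percentage points in the cases examined. Beyond that the problem recedes. This is a weakness in what the analysis reports and what may be concluded from it. It does not show that the sponsor intends to misread the result. It should be corrected before the data are analysed.

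**What to change.** In Data Analysis:

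1. Make the between-arm difference with its 95% CI the main result of each comparison: Newcombe or exact intervals for proportions, and t-based or Hodges-Lehmann intervals for continuous outcomes. The tests may stay as secondary output.
2. State that p > 0.05 will not be taken as evidence that NP-PWD is comparable to standard of care.
3. Require any conclusion that NP-PWD is an alternative to standard of care to quote the largest deficit that the interval still allows.

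This takes a few sentences and no extra subjects, visits or data. The price is that conclusions will look less certain, with intervals of about ±0.85 SD for continuous outcomes.

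No non-inferiority design or added enrolment is asked for. At one-sided 0.025, 80% power and no true difference, 12 per arm could support only a margin of (1.960 + 0.842) × √(2/12) = 1.14 SD. For proportions the margin would be about 34, 46 or 52 points at control success of 90%, 80% or 70%. Estimation is the realistic aim at this size.

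### CFU secondary objective: the plan offers only an unadjusted t or Wilcoxon test, although a pre-randomization swab is available for a between-arm ANCOVA of log10 CFU

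*Combined protocol and SAP*

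**What the plan says.** Section C3 lists CFU as a secondary objective: "To evaluate colony forming units present on study wounds before and after treatment(s". It names no comparator. The readiness objective beside it does: "To evaluate and compare wound readiness for closure between study wounds treated with NP-PWD versus SoC". The general aim in C3 is also comparative: "This study is intended to evaluate the feasibility of the NP-PWD as compared to SOC".

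Each subject has two swabs. Section D lists the first among the Day 0 activities, ahead of allocation: "wound swab for colony forming unit count, randomization, and application". The footnote to the Schedule of Events places the second: "The wound swab will be taken once at baseline and once at the time of final removal". The text of Section D agrees, attaching a final swab to the end of therapy, which can come early: "If negative pressure wound therapy is no longer indicated at any time after the minimum requirement of 2 has been met". The body of the schedule table, however, marks the second swab only at Visit 4 (Days 7-9), which is optional.

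The Data Analysis section does not mention CFU. For continuous variables it says "continuous variables will be compared via student-t test or Wilcoxon test as appropriate". The only model it names is "We plan to perform a forward stepwise logistic regression", with no outcome stated.

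**The concern.** The trial will hold a baseline count for each subject, listed before randomization, but the stated method does not use it. If baseline and final counts are correlated, an unadjusted test of the final count leaves explainable variance in the error term and gives no protection against chance baseline imbalance, which is easily large with 24 subjects. A test of change uses the baseline but does badly when the correlation is low. The plan does not choose between the two, so the choice can be made after the data are seen. The logistic regression does not fill the gap, because it does not give a baseline-adjusted comparison of a count.

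Two practical matters go with this. Swab counts can be zero or below the assay limit, and on a log scale the result then depends on an unstated substitution. And any baseline-to-final analysis needs a final swab from every subject, which the schedule table and its footnote do not place consistently.

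**Working it through.** The plan gives no figure to reproduce: 24 completed subjects are stated without effect size, SD, correlation, alpha or allocation ratio. Everything below is illustrative.

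**Inputs.** From the documents: 24 completed subjects, two randomized arms, one swab at baseline and one at final removal. Assumed: 12 per arm, all swab pairs complete, two-sided alpha 0.05, normal log10 CFU with equal SD (set to 1) at both swabs, and baseline-final correlation r.

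**Step 1: precision.** SD relevant to each analysis: final value 1; change √(2(1−r)); ANCOVA √(1−r²). Estimating the slope inflates the ANCOVA variance on average by 1 + 1/(24−4) = 1.05. The variance ratio of ANCOVA to final value is therefore 1.05(1−r²):
- r = 0: 1.05
- r = 0.3: 1.05 × 0.91 = 0.956
- r = 0.5: 1.05 × 0.75 = 0.788
- r = 0.7: 1.05 × 0.51 = 0.536

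Break-even is at 1−r² = 1/1.05, so r = 0.218.

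**Step 2: power.** Simulation, 100,000 runs per cell, final value / change / ANCOVA:

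| Effect | r=0 | r=0.3 | r=0.5 | r=0.7 | r=0.9 |
|---|---|---|---|---|---|
| 0.8 SD | 47/26/45% | 46/35/48% | 46/47/56% | 46/68/73% | 47/99/99% |
| 0.5 SD | 22/13/21% | 22/17/23% | 22/22/26% | 22/33/36% | 22/74/74% |
| 0.3 SD | 11/8/11% | 11/9/11% | 11/11/13% | 11/15/16% | 11/35/35% |

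Noncentral-t check at 0.8 SD. Final value: noncentrality 0.8/√(2/12) = 1.96 on 22 df, power 46.6%. ANCOVA at r = 0.5: 0.8/√(0.788 × 2/12) = 2.21 on 21 df, power 55.8%. ANCOVA is within about 2 points of the best method in every cell; final value and change each fall well behind somewhere.

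**Step 3: below-detection counts.** Limit set at the 30th percentile of baseline and control-arm final counts, half the limit substituted, SD of log10 CFU taken as 1, 0.8 SD effect. Final / change / ANCOVA: 40/20/38% at r=0, 40/25/41% at 0.3, 40/32/46% at 0.5, 40/46/59% at 0.7. The ANCOVA gain at r = 0.5 shrinks from about 10 points to 6.

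The substituted value matters. With non-detects at the final swab only (30% of control-arm counts, r = 0.5, 0.8 SD), substituting the limit, 1/2, 1/10 or 1/100 of it gives 20/27/39/46% for change and 42/46/48/47% for ANCOVA. Rank-based ANCOVA stays at 46%, because any common value below the limit gives the same ranks.

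**Step 4: an open choice.** With no true difference, reporting whichever of final value and change is significant gives type I error of 8.3/8.9/9.3/9.5% at r = 0/0.3/0.5/0.7.

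**Step 5: separate within-arm tests.** Suppose both arms have the same true fall. With p the power of a paired t test in 12 subjects (SD of change √(2(1−r))), exactly one arm is significant with probability 2p(1−p), which cannot exceed 50%. At r = 0/0.3/0.5/0.7:
- fall 0.2 SD: 14/15/18/23%
- fall 0.5 SD: 32/39/46/50% (11% at r = 0.9)
- fall 1 SD: 48/37/21/4%
- fall 1.5 SD: 15/4/1/0%

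**The case against.** The strongest reply is that a short generic rule suits a 24-subject feasibility study, and that the design and stated aim already point to a between-arm comparison. The t/Wilcoxon clause also sits beside a chi-square clause that would normally compare independent groups. This largely stands: between-arm is the likelier reading. It does not settle final value versus change, or the handling of non-detects, and it does not bring the baseline into the analysis.

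Second, the gain depends on r, which nobody has stated. At r of 0.3 or less it is at most about 2 points, and it is small at small effects. The estimate is imprecise in any case: the 95% CI half-width is 2.074 × √(2/12) = 0.85 SD unadjusted and 2.080 × √(0.788 × 2/12) = 0.75 SD with ANCOVA at r = 0.5. This stands, and is why the point should not be inflated.

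Third, the objective literally asks for before and after, and the documents do not dictate ANCOVA. That is fair: within-arm values should be reported, and ANCOVA is one sound choice among several. It is recommended because it is never far from the best when r is unknown.

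A reader might also infer that the plan will judge the device from separate within-arm tests, and that these would usually mislead. The documents propose no such inference, and Step 5 gives anything from about 0 to 50%, depending on the fall and on r.

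**Conclusion.** The concern holds as a matter of efficiency and pre-specification for one secondary outcome. Under the assumptions above, ANCOVA moves power at 0.8 SD by −2 points at r = 0, +2 at 0.3, +10 at 0.5 and +27 at 0.7, and by about +6 at r = 0.5 with 30% of baseline and control-arm final counts below detection. None of the inputs beyond the 24 subjects and the two-arm, two-swab design comes from the documents, so the direction is firmer than the size.

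Three stronger readings are not supported. The unadjusted between-arm test is not biased; randomization makes it valid. The 8-10% type I error describes selective reporting, which the plan permits by silence but does not propose. And the schedule conflict does not show that early finishers will lack a final swab, since the footnote and text place it at final removal; it shows that the passages disagree. The primary usability and feasibility objective is unaffected.

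**What to change.** Add a short paragraph to Data Analysis, before any outcome data are reviewed:

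- CFU is compared between arms by ANCOVA of log10 CFU at final removal on treatment and baseline log10 CFU. Report the adjusted difference with its 95% CI.
- State the laboratory's detection limit and one substitution value for zero or below-detection counts (for example, half the limit). Report the number of such counts by arm and swab.
- Use rank-based ANCOVA as the sensitivity analysis.
- Report before and after values within each arm descriptively, as the objective's wording asks.
- Report days on therapy at the final swab by arm, descriptively. The swab day varies and is determined after randomization, so it should not be a covariate.

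Separately, reconcile the Schedule of Events table with its footnote and the Section D text on when the final swab is taken, because the analysis needs one from every subject.

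Cost: one paragraph and one schedule correction, with no visits or swabs beyond the two already planned per subject. The statistical price is one degree of freedom and about 5% more variance if r is near zero (power 45% instead of 47% at 0.8 SD).
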